8.1.2 Availability

AT13387 (onalespib) is an investigational agent supplied to investigators by the Division of Cancer Treatment and Diagnosis (DCTD), NCI.

8.1.3 Agent Ordering and Agent Accountability

NCI-supplied agents may be requested by the responsible investigator (or their authorized designee) at each participating institution. Pharmaceutical Management Branch (PMB) policy requires that agent be shipped directly to the institution where the patient is to be treated. PMB does not permit the transfer of agents between institutions (unless prior approval from PMB is obtained). The CTEP-assigned protocol number must be used for ordering all CTEP-supplied investigational agents. The responsible investigator at each participating institution must be registered with CTEP, DCTD through an annual submission of FDA Form 1572 (Statement of Investigator), Biosketch, Agent Shipment Form, and Financial Disclosure Form (FDF). If there are several participating investigators at one institution, CTEP-supplied investigational agents for the study should be ordered under the name of one lead investigator at that institution.

Submit agent requests through the PMB Online Agent Order Processing (OAOP) application. Access to OAOP requires the establishment of a CTEP Identity and Access Management (IAM) account and the maintenance of an “active” account status, a “current” password, and active person registration status. For questions about drug orders, transfers, returns, or accountability, call or email PMB any time. Refer to the PMB’s website for specific policies and guidelines related to agent management.

The investigator, or a responsible party designated by the investigator, must maintain a careful record of the receipt, dispensing and final disposition of all agents received from the PMB using the appropriate NCI Investigational Agent (Drug) Accountability Record (DARF) available on the CTEP forms page. Store and maintain separate NCI Investigational Agent Accountability Records for each agent, strength, formulation and ordering investigator on this protocol

9. BIOMARKER, CORRELATIVE, AND SPECIAL STUDIES

Blood, bone marrow or lymph node biopsy sampling for malignant cells will take place prior to treatment initiation, on cycle 1 day 17-22, and at the time of disease progression for several biomarker studies. These will include immunohistochemical quantification of ALK in ALK+ ALCL, cyclin D1 in MCL, and BCL6 in DLBCL using established dilutions of CLIA-approved immunostains that have been calibrated to detect changes in protein levels, as well as immunoblotting of tumor samples for known HSP90 clients including CDK4, cyclin D1, AKT and pAKT, ERK and pERK, IKK α , BTK (in DLBCL and MCL), HSP70, ALK (in ALCL), and BCL6 (in DLBCL). Each of these proteins, with the exception of HSP70, are HSP90 clients and thus expected to decrease following treatment with the HSP90 inhibitor AT13387 (onalespib). HSP70 is known to increase in a compensatory fashion upon HSP90 inhibition. Thus, changes in these proteins detected by immunohistochemistry or immunoblotting would be proof of principle that we are indeed depleting expected targets. In addition we will perform whole exome sequencing (on pre-treatment and disease progression samples) and RNASeq (on pretreatment, day 17-22 and disease progression samples) to identify genetic and transcriptional markers of disease response and resistance.

9.1 Integral Laboratory or Imaging Studies

9.1.1 Immunohistochemistry for ALK (ALCL), cyclin D1 (MCL) and BCL6 (DLBCL)

Immunostains on pre-treatment samples are integral assays as they determine patient eligibility for this study (ALK for ALCL, cyclin D1 for MCL, and BCL6 for DLBCL). See Appendix C-E for standard operating procedures (SOPs) for ALK, cyclin D1 and BCL6 respectively. Because this immunostain is diagnostic in this lymphoma, it should by definition be positive in 100% of pre-treatment samples. Because the standard concentration of the stains used for ALK, cyclin D1 and BCL6 is very sensitive for these proteins (i.e., saturating) and therefore not very specific regarding their quantification, we performed several titrations of these immunostains on known ALK+ ALCL, MCL, and BCL6+ DLBCL to determine the lowest concentrations that maintain strong baseline staining but allow for detection of differences in protein levels following treatment with AT13387 (onalespib) and at the time of progression. For ALK, a dilution of

1:24,000 appears to be optimal, while for BCL6 and cyclin D1 optimal staining dilutions would be 1:2000 and 1:160, respectively. We will start with dilutions of 1:24,000 for ALK, 1:2000 for BCL6, and 1:160 for cyclin D1. However, if using those dilutions we are unable to adequately detect antigen in the pre-treatment tumor sample, we will use serial lower dilutions for optimization of that individual tumor specimen, using that same dilution for the subsequent on-treatment and time of progression tumor samples.

The pre-treatment biopsy and the time of progression biopsy are intended to establish a baseline level of staining for comparison and to assess whether these protein levels are again upregulated at the time of treatment progression, and therefore a measure of treatment resistance. We intend to evaluate these immunostains as an early marker of disease response and proof of concept that we are indeed achieving HSP90 inhibition and depleting the expected targets. Given that we see changes in the protein levels of HSP90 clients within 12 hours of exposure to HSP90 inhibitors *in vitro* and after 5 days of treatment with an HSP90 inhibitor *in vivo*, we expect to see differences in HSP90 protein levels early in treatment. The half life of AT13387 (onalespib) is between 6 and 12 hours and the dosing schedule to be used on this study is the twice weekly dosing for 3 weeks with one week off, or dosing on days 1 and 2, 8 and 9, and 15 and 16. We therefore plan to get a biopsy on day 17, within 24 hours of the 6th dose of the drug, but will allow for a biopsy up to day 22 to accommodate scheduling, weekends, and holidays. This biopsy schedule was based on the timing of biopsies done for pharmacodynamic evaluation of AT13387 (onalespib) on the first-in-human phase I study that was recently reported.⁶⁶

We will use an automated Aperio measurement to determine an automated H-score, which previously has been found to be highly concordant with manual H-score determination ($R^2=0.8795$ for immunostains for MSI2 in AML for example).¹⁰³ Specifically, the assessment of the percentage of tumor cells that is positive for the immunohistochemical stain will be quantitative/continuously distributed from 0 to 100%, whereas the intensity of staining in a given sample will be graded from 0-3+ (0=no staining, 1=weak staining, 2=moderate staining, and 3+=strong staining). An H-score, the product of the percentage of positive tumor cells and the grade of staining intensity, will be calculated (range 0-300).¹⁰³ A reduction in the H-score of >50% will be considered meaningful. While the biomarker is integral at diagnosis and study entry, the comparison of quantitative changes in these biomarkers and response is exploratory and our statistical analysis will be descriptive. If there is a correlation between the comparative H-scores and treatment response, this provides a readily available standardized and technically feasible way to predict response to treatment early in a patient's treatment course.

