Results from the first-in-human phase 1 study of AT13387 (onalespib) in advanced solid tumors identified a maximally tolerated dose of 120mg/m² twice weekly for 3 weeks every 28 days, or 260mg/m² weekly for 3 weeks every 28 days.⁶⁶ One dose-limiting toxicity (DLT) of visual disturbance occurred at the 120 mg/m² twice-weekly schedule, and accordingly was declared the RP2D on the twice-weekly administration schedule. No formal DLTs occurred on the once-weekly schedule, though multiple severe toxicities, including diarrhea, nausea, vomiting, fatigue, and systemic infusion reactions, led to selection of 260 mg/m² as the RP2D on the once-weekly administration schedule. Sixty-two patients with a variety of solid tumors were treated, with one partial response in an imatinib-resistant gastrointestinal stromal tumor (GIST). Stable disease was observed in 36% of patients, one-third of whom experienced disease stabilization for over 4 months.

It has been shown with other HSP90 inhibitors, like ganetespib, that although once weekly dosing results in a prolonged intertumor $\frac{1}{2}$ life, the effect on downregulation of client proteins is short lived, with an initial protein depletion at 24 hours post-dosing followed by a steady increase to normal protein levels at 48-72 hours.⁶⁸ Furthermore, once weekly dosing results in a tumor growth delay with a transient reduction in client protein levels, while consecutive daily dosing (5 days in this study) results in tumor regression with a persistent reduction in client protein levels out to 168 hours. It has been difficult to do daily dosing of HSP90 inhibitors over 5 consecutive days in humans due to toxicity, so dosing over 2 consecutive days has been adopted. For AT13387, this dosing schedule was explored in a phase 1 study in solid tumors and the RP2D was 160mg/m² on d1, 2, 8, 9, 15, and 16 of a 28 day cycles and this dosing schedule was safe and tolerated.⁶⁷ Given the high proliferative index of the lymphomas included in this study, the variable sensitivity of their pathogenic HSP90 clients to HSP90 inhibition, and the target suppression advantage of consecutive day dosing, we chose to use this schedule in this lymphoma study.

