5. TREATMENT PLAN

5.1 Agent Administration

Treatment will be administered on an outpatient basis. Reported adverse events and potential risks are described in Section 7. Appropriate dose modifications are described in Section 6. No investigational or commercial agents or therapies other than those described below may be administered with the intent to treat the patient's malignancy.

Regimen Description					
Agent	Premedications Precautions	Dose	Route	Schedule	Cycle Length
AT13387 (onalespib)	No premedications are required	160mg/m ² in 250 cc 5% dextrose or 0.9% NS	IV over 1 hour	Days 1, 2, 8, 9, 15 and 16	28 days (4 weeks)

Patients will be dosed at 160mg/m²/dose on days 1, 2, days 8, 9, and days 15, 16 of a 4 week cycle. There will be a response assessment by PET/CT and CT scans every 2 cycles. If the CT portion of the PET/CT is of diagnostic quality, then an additional CT scan is not necessary. However, if CT portion of the PET/CT is a low-resolution CT, then a separate CT scan is necessary.

Treatment can be moved up or delayed to accommodate holidays, inclement weather, or other reasons for clinic closures. Patients can continue on treatment as long as they are responding and tolerating treatment. However, all patients will have to come off this study treatment by May 31, 2020, as the study treatment will no longer be available.

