5.1.1 AT13387 (onalespib)

The study drug AT13387 (onalespib) will be administered by intravenous infusion via peripheral or central venous access at a dose of 160mg/m² (using actual body weight from cycle 1 day 1 to calculate body surface area) over 1 hour. The dosing frequency will be on days 1, 2, 8, 9, 15, and 16 of every 4 week cycle. AT13387 (onalespib) will be provided by CTEP.

On the first day of treatment each week (days 1, 8, and 15), patients must meet the following pre-treatment criteria: ANC \geq 1000/mcL, platelet count $>$ 75,000/mcL (or $>$ 30,000/mcL if due to disease), potassium and magnesium above the institutional lower limit of normal (repletion is allowed).

Astex has recommended that vital signs (temperature, heart rate, blood pressure, oxygen saturations) be performed pre-AT13387 (onalespib) infusion. Additional vital signs will be performed during the course of infusion as clinically indicated. No extended post-administration monitoring will be required, except as indicated in the protocol for research-related assays.

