9.2 Exploratory/Ancillary Correlative Studies

9.2.1 Immunoblotting for HSP90 clients

We have extensive experience in the [name] lab with immunoblotting for several HSP90 clients in MCL and DLBCL cell lines before and following exposure to HSP90 inhibitors, and in tissue from MCL cell line and patient derived xenografts treated with either vehicle or drug (see section 2.3.2). These include BTK and pBTK, cyclin D1, CDK4, AKT and pAKT, ERK and pERK, IKK α , p100, p52, and BCL6. Our lab will immunoblot for these HSP90 clients and

others, and compare protein levels semi-quantitatively between pre- and on-treatment lymphoma cells, and at the time of disease progression. We expect to see downregulation of these proteins on treatment, and possibly upregulation of some or all of these proteins at the time of progression on drug.

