9.2.2 Whole exome sequencing and transcriptome analysis

Samples will also be submitted for whole exome sequencing (with paired germline samples) and RNAseq, and results will be compared between pre- and on-, and time or progression tumor samples for markers of disease response and resistance. For exome sequencing, the ABSOLUTE algorithm will be applied to determine the cancer cell fraction. Variant allele fractions for mutations present in the progression sample can then be compared to those in the pre-treatment sample after adjustment for cancer cell fractions to determine whether AT13387 (onalespib) results in a shift in the clonal architecture of lymphomas.⁸⁵ Although HSP90 classically acts at the post-translational level, some evidence indicates that it also can affect transcription.⁸⁶ We previously demonstrated in human leukemia cells that transcriptional profiling can highlight downstream pathways that are suppressed or activated in response to the degradation of HSP90 clients.⁸⁷ Transcriptional analysis by RNAseq will be performed on specimens obtained prior to beginning treatment, during treatment with AT13387 (onalespib) and then upon progression. In cases with bone marrow or peripheral blood involvement, lymphoma cells will be purified, for example by CD19 selection. Markers of response and progression will be determined by: 1) comparing gene expression patterns using GSEA⁸⁸, 2) interrogation of the Broad Institute Molecular Signatures Database⁸⁸ (MSigDB; <http://www.broadinstitute.org/gsea/msigdb/index.jsp>) and 3) Ingenuity Pathway Analysis^{89,90}, as we previously performed.⁹¹ In addition, we will interrogate the signature of progression during AT13387 (onalespib) treatment in the Connectivity Map, a database linking gene expression with drug sensitivity.⁹² Build 2.0 contains over 7,000 expression profiles representing the effects of 1,309 compounds. Compounds that correlate inversely with the signature, and therefore may abrogate it, are readily available therapeutics to block pathways that bypass HSP90 inhibition. The analysis of these exploratory biomarker studies will be retrospective, with assays performed after response evaluation for biomarker identification.

If new health information about inherited traits is found on research testing, the study doctor will let the participant know about this and the participant will then be able to choose whether or not to receive this information.

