10. STUDY CALENDAR

Baseline evaluations are to be conducted within 2 weeks prior to start of protocol therapy. Scans and x-rays, including LVEF evaluation, must be done ≤ 6 weeks prior to the start of therapy and bone marrow biopsy must be done ≤ 6 weeks prior to the start of therapy. In the event that the patient's condition is deteriorating, laboratory evaluations should be repeated within 48 hours prior to initiation of the next cycle of therapy.

		Cycle 1								Cycle 2+		
	Pre-Study ^a	D 1	D 2	D 8	D 9	D 15	D 16	D 17	D 18	D 1,8,15	D 2,9,16	Off Treatment ⁱ
AT13387 (onalespib)		A	A	A	A	A	A			A	A	
Informed consent	X											
Demographics	X											
Medical history	X											
Detailed eye exam ^b	X											
Concurrent meds	X	X-----X										
Physical exam	X	X		X		X				X		X
Vital signs	X	X	X	X	X	X	X			X	X	X
Height	X											
Weight	X	X	X	X	X	X	X			X	X	X
Performance status	X	X		X		X				X		X
CBC w/diff, plts	X	X		X		X		X		X		X
Serum chemistry ^c	X	X		X		X		X		X		X
EKG ^d	X	X		X		X				X ^d		X
LVEF evaluation (TTE or MUGA)	X											
Adverse event evaluation ^e		X-----X										X
Bone marrow biopsy	X											X ^f
Blood sample for germline sequencing ^g	X											
Radiologic evaluation												
FDG-PET/CT scans	X									FDG-PET/CT should be performed every 8 weeks +/- 3 days		X
CT chest/abdomen/pelvis	X									CT scans should be performed every 8 weeks +/- 3 days		X ⁱ
B-HCG ^h	X											
Tumor biopsy ^k	X							X				X

A: AT13387 (onalespib): 160mg/m²/dose as assigned
a: All screening must take place within 2 weeks of the start of therapy, except for scans, which must occur within 6 weeks, and the screening bone marrow biopsy, which must occur within 6 weeks, prior to the start of therapy.
b: All patients will have a detailed eye exam by an ophthalmologist during screening to be used as a baseline eye exam for comparison, should ocular toxicity later develop. There are no protocol-specific tests required for this eye exam. If patients develop eye symptoms during treatment, an additional eye examination may be conducted at the investigator's discretion. See appendix I for an example of an eye exam work-up. Using this eye exam form is *not* required.
c: Albumin, alkaline phosphatase, total bilirubin, bicarbonate, BUN, calcium, chloride, creatinine, glucose, LDH, phosphorus, potassium, magnesium, total protein, SGOT [AST], SGPT [ALT], sodium, uric acid.

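### Renewed client-protein expression (or RNA change) in the progression biopsy is read as resistance, but time off drug is not controlled and washout could produce the same result

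*Combined protocol and SAP*

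**What the plan says.** Section 9.1.1 gives the progression biopsy an interpretive role. With the pre-treatment sample as baseline, it is intended "to assess whether these protein levels are again upregulated at the time of treatment progression, and therefore a measure of treatment resistance". Section 9.2.1 expects lower client levels on treatment and "possibly upregulation of some or all of these proteins at the time of progression on drug". For RNA, Section 9.2.2 states that "we will interrogate the signature of progression during AT13387 (onalespib) treatment in the Connectivity Map", to find compounds that block pathways bypassing HSP90 inhibition.

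On timing, Section 5.1.1 states that "The dosing frequency will be on days 1, 2, 8, 9, 15, and 16 of every 4 week cycle". Section 5.1 says "There will be a response assessment by PET/CT and CT scans every 2 cycles", and the study calendar in Section 10 says "FDG-PET/CT should be performed every 8 weeks +/- 3 days". Progression ends treatment (Section 5.3), and the calendar places the final tumor biopsy in its off-treatment column.

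The on-treatment biopsy is timed to the drug. Section 9.1.1 notes that "The half life of AT13387 (onalespib) is between 6 and 12 hours" and sets the biopsy for day 17, within 24 hours of the sixth dose, with day 22 as the latest date. Neither Section 9 nor the calendar sets a time from last dose for the progression biopsy, and no analysis takes that time into account.

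**The concern.** HSP90 clients are expected to fall while the drug acts and to recover once it is gone. If the on-treatment sample is taken shortly after a dose and the progression sample well into the treatment-free part of the cycle, the two differ systematically in drug exposure as well as in disease course. Recovery of ALK, cyclin D1 or BCL6 at progression could then mean that the tumor escaped inhibition, or only that dosing had stopped.

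The plan adopts the first reading without a means of excluding the second. At stake are exploratory objectives 1.3.1 (on-target activity) and 1.3.2 (markers of response and resistance). Section 13.1 also names the baseline, on-treatment and progression levels of these three proteins as primary endpoints of the laboratory component. A resistance claim from this comparison could be wrong, and a Connectivity Map signature that included withdrawal effects could point to the wrong bypass pathways.

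**Working it through.** **Inputs**
- Dosing days 1, 2, 8, 9, 15 and 16 of 28 (Section 5.1.1).
- Scans every 2 cycles, or 8 weeks ± 3 days (Sections 5.1 and 10).
- On-treatment biopsy on day 17, allowed to day 22 (Section 9.1.1).
- Client proteins after once-weekly dosing of another HSP90 inhibitor: depletion at 24 h, "followed by a steady increase to normal protein levels at 48-72 hours" (Section 2.2.1.1).
- Client proteins after five consecutive daily doses: still reduced at 168 h, with no later time reported (same section).
- Half-life 6–12 h (Section 9.1.1); longest individual value 14 h (Section 2.2.1.1).

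**1. The plan's own figure.** The sixth dose is on day 16. Day 17 − day 16 = 1 day, which agrees with Section 9.1.1. At the end of the window, day 22 − day 16 = 6 days. The on-treatment sample is therefore 24 to 144 h after a dose. The plan states no corresponding figure for progression.

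**2. Progression at a scheduled scan, next cycle not yet dosed.** Study day = 28 × (cycle − 1) + cycle day.
- Last dose of cycle 2: 28 + 16 = day 44.
- Scan at day 56 ± 3, that is day 53 to 59.
- Gap: 53 − 44 = 9 days to 59 − 44 = 15 days.
- If 8 weeks is counted to day 57 (cycle 3 day 1), the gap is 10 to 16 days.
- The second restaging gives the same values: last cycle 4 dose on day 100, scan on day 109 to 115, gap 9 to 15 days.

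These gaps run to the scan. Reading it and booking the biopsy add to them.

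**3. Against the cited recovery times.** Nine days = 216 h. 216/72 = 3 and 216/48 = 4.5, so the shortest scheduled gap is 3 to 4.5 times the cited recovery time. It is also 216 − 168 = 48 h beyond the last time at which suppression is reported.

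**4. Half-lives, plasma only.** 216/12 = 18 and 216/6 = 36; at 14 h, 216/14 = 15.4. Little drug would remain in plasma. This is not a tumor measurement.

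**5. Other routes to progression**
- Scan after cycle 3 has started on day 57: a scan on day 58 or 59 is 1 day after a dose, and one on day 60 is 2 days after.
- Between scans: in a cycle given on schedule, only days 25 to 28 (gaps of 9 to 12 days) and day 1 before dosing (13 days) lie 9 or more days after a dose. That is 5/28 = 18% of cycle days, before any biopsy delay.
- After stopping for another reason: CT at 6 and 12 months (Section 5.4), so any biopsy then would be long after the last dose.

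The progression samples can thus be a mixture of on-drug and off-drug states. The documents do not give the proportions.

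**The case against.** A reader might infer that rebound in these samples shows washout and not resistance. The documents do not support that.
- The 168 h figure is the last time reported, not a ceiling on suppression.
- Both recovery figures come from another inhibitor, and the 48–72 h figure comes from once-weekly dosing. The plan chose two consecutive days for a claimed advantage in target suppression and gives no recovery time for onalespib on that schedule.
- The half-life is from plasma. The same background text mentions a prolonged half-life in tumor for such drugs, although it adds that the effect on client proteins is nonetheless short-lived.

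Three further inferences also go too far. First, the gap of at least 9 days applies to detection at a scheduled scan before the next cycle, and nothing shows how common that is. Second, Section 5.4 and the calendar notes list only CT for patients who stop without progression; whether they are biopsied later is unclear. Third, Section 9.2.2 does not say which contrast defines the Connectivity Map signature, so harm there is possible, not established.

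It can also be said that Section 13.1 already reports changes as differences and as proportions of baseline, including at progression. The Wilcoxon test there compares responders with non-responders, and Section 9.1.1 calls the comparison of biomarker change with response exploratory and descriptive.

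These points limit the claim and its reach. They do not remove the stated inference, the wording that places progression on drug, or the missing time variable.

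**Conclusion.** The concern holds as confounding. For progression found at a scheduled scan before the next cycle is dosed, the biopsy is at least 9 to 15 days after the last dose, against 1 to 6 days for the on-treatment sample. That exceeds both times in the protocol's own background, so renewed client expression, and any RNA change relative to the on-treatment sample, cannot be told apart from washout. Section 9.1.1 nevertheless treats it as a measure of resistance.

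This rests on dosing and scanning to schedule, and on the other inhibitor's data being the only guide to recovery that the documents offer. The effect is confined to the exploratory protein and RNA objectives. Exome comparisons, the overall response rate and the two-stage rules are untouched. A correction is worth making because the plan states the unsupported conclusion in advance.

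**What to change.** 1. Derive the time from last dose to every biopsy from the dosing and biopsy dates, in hours where clock times exist. Report progression H-score, immunoblot and RNAseq results by that interval.
2. In Section 9.1.1, remove the automatic inference that re-upregulation measures resistance. In Sections 9.2.1 and 9.2.2, remove the wording that places progression on drug or during treatment for samples taken off drug.
3. Use progression versus pre-treatment as the resistance-associated contrast, including for the Connectivity Map signature, only for progression samples taken off drug beyond a prespecified interval. The documents do not determine that interval, so state it as an assumption. Applying this contrast to every progression sample would be wrong: one taken 1 or 2 days after a cycle 3 dose could differ from baseline through drug effect alone.
4. Use progression versus on-treatment only for progression samples taken at a comparable time after a dose.
5. Report the remaining samples descriptively, without a resistance label.

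The cost is revised wording in Section 9, a matching sentence in Section 13.1 and one derived variable. No new samples are needed, and Section 9.2.2 already makes these exploratory biomarker analyses retrospective. The downside is that samples taken off drug, probably most of them if progression is mainly found at scheduled scans, can no longer be offered as evidence on whether suppression persisted on drug. The resulting subsets will also be small, given planned cohorts of 10, 20 and 20.
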